#### *Questionnaires variables*

The PCS and central CSI questionnaires will be completed before the beginning and upon completion of the study (Cuesta-Vargas et al., 2016; Garcia Campayo et al., 2008). Both these variables will be introduced as predictors in the regression model, due to their intrinsic association with a CS phenotype. The PCS will be used to identify specific pain cognitions that are usually present in patients with a CS phenotype, this measure will be used to evaluate the association of CLBP with psychosocial factors described by Smart et al. (Smart, et al., 2012). The CSI is an excellent tool to identify patients compatible with CS mechanisms, particularly when using the cut-off value of 40/100 (Scerbo et al., 2018). Pre and post reference values of these questionnaires will be taken from the healthy population sample in the same time-frame.

In addition, the Beck Depression Inventory II (BDI-II) and the Generalized Anxiety Disorder scale (GAD) questionnaires will be used to screen and quantify symptoms of depression and anxiety (García-Campayo et al., 2010; Sanz et al., 2005). The scores in these questionnaires will be measured both at baseline and follow-up for exploratory purposes and to determine whether significant correlations exist between any of these variables and the primary outcomes of pain and disability.

#### *Quantitative sensory testing*

Once the clinical examination and questionnaires have been completed, quantitative sensory testing (QST) based on the German protocol (Rolle et al., 2006; Starkweather et al., 2016) will be performed with the aim of evaluating thresholds and sensitivity to pressure pain and PPTs (see Figure 1–2). QST will consist of the exploration of the PPTs in deep tissues, using an algometer (Wagner Force Dial FPX, Greenwich, CT, USA). In addition to examining the pain detection threshold, patients will assess the intensity of the first stimulus above threshold, using a numerical rating scale between 0 (no pain) and 100 (maximum pain imaginable) (Pfau et al., 2014). Two measurements will be taken twice bilaterally at a rate of about 50 kPa/s, and the arithmetic mean of both the thresholds and sensitivities reported will be calculated. Two repetitions of these measurements provide excellent reliability in a population with LBP (Balaguier et al., 2016), while performing two repetitions per side of the lower back has been proposed to optimize inter-session reliability (Liew et al., 2021). PPTs will be performed over muscle tissue in 4 different locations. The main one will be 2.5 cm lateral to the spinous process in the erector spinae (Pfau, et al., 2014) of the vertebral segment with the highest clinical pain indicated by the patient and verified by palpation. This will allow the local segmental sensitivity to be assessed, which will be used as the predictor in the multiple regression model. These variables have been extensively studied in relationship to CS mechanisms in a CLBP population (den Bandt et al., 2019; Shraim, et al., 2021). In addition, for exploratory reasons, PPTs will be measured in the erector spinae four to six segments cranial to the most painful lumbar segment (heterosegmental sensitivity in a non-symptomatic segment: secondary hyperalgesia), on both lower limbs in the dermatome corresponding to the segment of highest clinical pain (dermatomal sensitivity), and in a control zone in both thenar eminences (widespread sensitivity). PPTs will be assessed during the initial examination and at the end of the study (see Figure 1). Reference values

will be taken in healthy volunteers in the same locations (lumbar segmental, heterosegmental, dermatomal, widespread) and the same time frame.

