### Patient sample

For this study, participants will be recruited through the network of contacts of MCC and the Chiropractic Research Network. To be included in the study, patient participants must be of legal age (18-70 years old), receive a diagnosis of primary CLBP of at least 3-month duration, with or without leg pain (according to a clinical examination carried out at the Madrid College of Chiropractic – MCC). If pain affecting the low back or lower limb is suspected to be predominantly of neuropathic origin, the patient will be excluded (Kosek et al., 2021). Additionally, patients will be excluded from the study if they present any of the following criteria: evidence of specific pathology as the cause of their CLBP, diagnosis of mental illness or pain of equal or higher intensity affecting the hand / thumb or regions near the lumbar spine, use of corticosteroids, opiates or anti-cytokine medication, pregnancy, lumbar fusion surgery or recent laminectomy, having received SMT in the 12 months prior to the beginning of the study (Gerhardt et al., 2017; Klyne et al., 2019; Smart et al., 2012). The only exception to this will be patients with a diagnosis of anxiety and depression, as these conditions are very frequently comorbid with CLBP (Gore et al., 2012; Wong et al., 2021) and may also suggest a CS phenotype (Aoyagi et al., 2019; Smart, et al., 2012). Candidates interested in participating in the study will initially complete a questionnaire with the selection criteria, either in person at the MCC or online. If the criteria are met, patients will be scheduled an appointment where they will be provided with an information sheet so that they can read all the information in detail and ask any questions they see fit, before signing the informed consent. Subsequently, they will be referred for a clinical examination (consisting of a case history and physical examination) that will confirm the diagnosis of primary CLBP (see Figure 1–0).

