### *Clinical examination variables*

During the case history taken, data on the characteristics of the patients' CLBP will be collected. Pain intensity will be the main primary outcome. Patients will evaluate the intensity of their CLBP at the current time, as well as the mean, minimum and

maximum pain throughout the preceding seven days or since the time of the previous session, once the study is underway, according to the brief pain inventory (de Andres Ares et al., 2015; Tan et al., 2004). Pain intensity will be collected via an online questionnaire without the presence of any investigator in every visit for descriptive reasons, although only the baseline and the final values will be used for statistical analyses. The other primary outcome will be the degree of disability provoked by CLBP. Upon completing the case history, patients will fill out the Oswestry low back disability index questionnaire (Alcántara-Bumbiedro et al., 2006), which will also be completed at the end of the study.

Additionally, other pain variables will be recorded at baseline for exploratory purposes: CLBP trajectory (duration and frequency) and localization. For the later, patients will draw the area affected by their pain on a tablet, using an application (Symptom Mapper) that will allow the degree of widespreadness of their pain to be calculated (Ellingsen et al., 2021). They may also indicate any pain present of less intensity outside the low back region, as any symptom of higher intensity will necessarily exclude the patient from the study. Additionally, clinicians will determine whether the CLBP is proportionate or disproportionate to the degree or nature of the injury or pathology, with a discrete or rather diffuse distribution, according to criteria that have been defined in the literature (Nijs et al., 2015; Smart, et al., 2012). A diffuse rather than a discrete distribution has been identified as a key criterion suggesting a CS phenotype (Kosek, et al., 2021; Smart, et al., 2012).

Finally, other variables will be reported such as the intake of pain medication compatible with the selection criteria, both at baseline and at the end of treatment. Similarly, whether the patient regularly smokes will be reported at baseline, since smoking has been associated with increased serum levels of pro-inflammatory cytokines.

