(Petrescu et al., 2010), and the average number of hours of sleep which may help predict pain patterns and will be used for exploratory purposes (Edwards et al., 2008). Additionally, the presence of any chronic conditions (including pain conditions) that is comorbid with the CLBP will be recorded for exploratory purposes.

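### The cranial and thenar pressure pain sites are read as non-symptomatic and control sites, but nothing checks that they are pain-free, so local tenderness can count as secondary or widespread hyperalgesia in the exploratory comparison with healthy volunteers.

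*Protocol*

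**What the plan says.** The protocol's section on quantitative sensory testing names four PPT locations. The main one is the most painful segment, and it alone feeds the regression. The other three are exploratory, each with its own interpretation:

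- Cranial erector spinae: "four to six segments cranial to the most painful lumbar segment (heterosegmental sensitivity in a non-symptomatic segment: secondary hyperalgesia").
- Thenar eminences: "in a control zone in both thenar eminences (widespread sensitivity").
- Legs: "on both lower limbs in the dermatome corresponding to the segment of highest clinical pain (dermatomal sensitivity").

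Healthy volunteers are measured at the same four locations.

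On eligibility, the section on the patient sample excludes "pain of equal or higher intensity affecting the hand / thumb or regions near the lumbar spine" and admits "primary CLBP of at least 3-month duration, with or without leg pain". The section on clinical examination variables says of the pain drawing: "They may also indicate any pain present of less intensity outside the low back region". It adds that "the presence of any chronic conditions (including pain conditions) that is comorbid with the CLBP will be recorded for exploratory purposes". Volunteers, by contrast, must have no current or chronic pain condition (Protocol, Healthy population sample).

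The last paragraph of the SAP compares PPTs between controls, SMT and placebo by mixed analysis of variance, to establish whether patients show raised pain sensitivity and hyperalgesia. It does not say which PPT sites enter.

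**The concern.** A low PPT in a region that does not hurt suggests altered processing beyond the painful area. A low PPT in a region that does hurt may be no more than local tenderness. The labels on the cranial and thenar sites presume the first case, while the entry criteria allow the second.

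Randomisation should balance pain at the test sites between SMT and placebo. It cannot do so between patients and volunteers, because volunteers are selected to be free of pain. Any contamination therefore lowers the patient values only. At stake is whether a patient-healthy difference at these two sites can be reported as secondary or widespread hyperalgesia, in a trial whose organising idea is central sensitization.

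**Working it through.** **Step 1. Labels against entry criteria.**

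- *Thenar site.* Hand or thumb pain excludes a patient only if it is at least as strong as the back pain. A patient with weaker hand pain is eligible and is tested at a site called a control zone.
- *Cranial site.* Weaker pain near the lumbar spine is also allowed. In addition, the back pain itself may reach the site. Counting up from L5 gives L4, L3, L2, L1, so the fourth segment is L1, which is still lumbar. This applies when L5 is the most painful segment and the nearest permitted level is chosen; five or six segments above L5 is T12 or T11. The exclusion for other pain says nothing about how far the index pain extends.
- *Leg site.* Leg pain is allowed, but the label is dermatomal sensitivity of the painful segment. It does not presume a pain-free site, so there is no conflict.

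The painful segment is verified by palpation. No matching check is written for the remote sites. The pain drawing, comorbid pain conditions and leg pain are recorded, but none is tied to the PPT sites or their analysis.

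The two eligibility statements also differ. The patient-sample section excludes pain of equal or higher intensity; the clinical-examination section mentions only higher intensity. They should be reconciled. Lesser pain is admitted under either.

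**Step 2. Possible size.** The plan gives no figure on this point: no prevalence of pain at a test site and no PPT standard deviation. Only the group sizes come from the documents (Protocol, Sample size calculation): 5 predictors × 10 = 50 per arm, so 2 × 50 = 100 patients, plus 50 volunteers.

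Assumed: a proportion p = 0.1 to 0.3 of patients has pain at a given site, and it lowers the PPT there by d = 0.5 to 1.0 SD.

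Shift in the patient mean = p × d.

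Standard error in SD units: √(1/100 + 1/50) = 0.173 for all patients against volunteers; √(1/50 + 1/50) = 0.200 for one arm against volunteers.

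Chance of a significantly lower patient PPT with no central mechanism = Φ(shift/SE − 1.96), two-sided 5% test, nominal 2.5% in that direction.

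| p | d (SD) | Shift (SD) | 100 v 50 | 50 v 50 |
|---|---|---|---|---|
| 0.1 | 0.5 | 0.05 | 4.7% | 4.4% |
| 0.1 | 1.0 | 0.10 | 8.3% | 7.2% |
| 0.2 | 0.5 | 0.10 | 8.3% | 7.2% |
| 0.2 | 1.0 | 0.20 | 21.0% | 16.9% |
| 0.3 | 0.5 | 0.15 | 13.7% | 11.3% |
| 0.3 | 1.0 | 0.30 | 41.0% | 32.3% |

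If the two sides are averaged and the pain is always on one side, each shift halves, to 0.025 to 0.15 SD.

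**Step 3. Limits of these percentages.** They describe a single-visit comparison of two means with equal SDs. The SAP plans a mixed analysis of variance in which only significant effects are decomposed, and that gate lowers the percentages. A group effect averaged over two visits raises them if the pain persists: with a correlation of 0.5 (the protocol's assumption for the main outcomes, borrowed here), the standard error is multiplied by √((1 + 0.5)/2) = 0.866. The range of shifts is the firmer result; the percentages are illustrations.

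**The case against.** The strongest objection is that pain at a remote site need not be a contaminant. The protocol treats diffuse pain as a key sign of the central sensitization phenotype and takes the drawing partly to measure widespreadness. Dropping every painful site could remove the patients who show that phenotype most clearly, and bias the comparison towards no difference. This stands. It rules out making the pain-free subset the main analysis, and it means a low PPT at a painful remote site cannot simply be called false. It does not rescue the labels: at a painful site the PPT alone cannot separate the two explanations.

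A second objection is that the plan has anticipated the problem. It names hand and thumb pain in the exclusions, and the non-symptomatic wording could be a condition for choosing among the fourth to sixth segments. Both are fair readings. But the exclusion stops at the intensity of the back pain, and no verification step is written for the segment.

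A third is reach. Remote PPTs are exploratory, and the SAP paragraph names no remote site. The sample-size section describes reference values for the predictor variables, whose PPT is the local one. This limits the importance. Even so, volunteer values are collected at all four locations, so a comparison at the remote sites is evidently intended.

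A reader might also infer that the leg site has the same fault, or that the trial's main results are biased. The documents support neither. The leg site is not presented as pain-free; the regression uses only the PPT at the primary pain area; and the primary outcomes are pain intensity and disability.

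**Conclusion.** The point holds for the cranial and thenar sites, in the exploratory comparison of patients with healthy volunteers. There the plan cannot tell local tenderness from secondary or widespread hyperalgesia, and the error can run only towards finding hyperalgesia.

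Its size cannot be fixed from the documents. Under the assumed 10% to 30% prevalence and 0.5 to 1.0 SD reduction, the patient mean shifts by 0.05 to 0.30 SD, less with one-sided pain and averaged sides. At the low end this is negligible; at the high end it could produce a significant difference by itself.

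The primary outcomes and the regression do not use these sites, and randomisation should protect the SMT-placebo contrast. This is a cheap improvement in what the trial can conclude, not a flaw in its main analyses.

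**What to change.** - *Protocol, Quantitative sensory testing:* code each cranial and thenar site, by side, as inside or outside the Symptom Mapper pain area at baseline.
- *SAP, paragraph on the comparison with healthy controls:* state that the remote PPTs are included and keep all sites in the main analysis. Add a prespecified sensitivity analysis using only pain-free sites, taking one side where only one is pain-free. Describe a difference as secondary or widespread hyperalgesia only if the estimate is similar at the pain-free sites.
- *Leg site:* leave it as dermatomal sensitivity, optionally described by presence of leg pain.
- *Protocol, Patient sample and Clinical examination variables:* reconcile the two statements of the intensity threshold for exclusion.

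The cost is one coded item per site from a drawing already taken, some SAP wording, and less precision in the sensitivity analysis. The pain-free subset may under-represent patients with widespread pain, which is why it should support the main analysis and not replace it.

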#### *Laboratory tests: inflammatory biomarkers in urine*

Before initiating the first treatment session and on the day of the last one, urine samples will be collected from all patients (first morning micturition), which will be immediately stored at -20°C (see Figure 1–1). Additionally, the first morning micturition will be collected twice from healthy individuals in the same timeframe (two samples with a 4-week delay). Urine concentrations of tumor necrosis factor alpha (TNF- $\alpha$ ) will be measured. For each sample, the urine concentrations of each cytokine (in pg / ml) and creatinine (mg / dl) will be measured. The cytokine to creatinine ratio (in pg / mg) will be calculated to correct for differences in urine volumes (Ortega et al., 2019). TNF- $\alpha$  values will be used for the regression model, since it has been repeatedly found to be elevated in CLBP patients and may respond to a treatment based on SMT (Lim et al., 2020; Morris et al., 2020; Teodorczyk-Injeyan et al., 2006; Teodorczyk-Injeyan et al., 2021).

#### *Expectations and effectiveness of the blinding*

Before initiating treatment, each participant will be asked about their expectations of pain relief upon completion of the study. To do this, they will give a verbal evaluation using an analog scale with the descriptors -100, equivalent to "total pain relief," 0, equivalent to "no change," up to +100, equivalent to "maximum pain increase". Expectations of pain relief will be used as the fifth predictor in the regression model, allowing to identify the contribution of patients' expectations, which as an important part of the placebo effect and may predict the response to treatment for chronic pain (Cormier et al., 2016).

In addition, in order to confirm the efficacy of the placebo intervention, the participants will respond before the second, seventh and last (twelfth) sessions to the following question: “Do you think that the treatment you have received is a real chiropractic treatment for back pain?”. A second question will ask patients about the degree of certainty with respect to the previous question on a numerical rating scale of 0–10, with 0 being total uncertainty and 10 being absolute certainty (Chaibi et al., 2015). These questions will be answered in an online questionnaire without the presence or interference of any investigators. Potential differences to these questions between the two groups will be examined.

#### *Adverse events reporting*

At the beginning of any of the follow-up SMT or placebo sessions, each patient will complete an online questionnaire without the presence of the investigator, answering whether they have suffered any adverse effects that they feel could be related to the treatment received. A clinical trial identified the following adverse effects as those most commonly reported after chiropractic treatment based on lumbar SMT: muscle stiffness, increased pain, radiating discomfort, and others (Walker et al., 2013). Following the example of this study, adverse effects will be classified into these categories, in addition to indicating whether they were triggered immediately, up to 24 hours, or more than 24 hours after the previous session, whether their duration was of minutes, hours (< 24 hours), between 24 and 48 hours, or longer than 48 hours (Walker, et al., 2013), and according to their intensity (very mild, mild, moderate, severe, very severe). A 3-point increase in the NRS-11 or the reporting of moderate to severe adverse events in three consecutive visits will raise the alert and the patient will be interviewed to determine whether care should be interrupted.

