## **Procedures**

The study will have a total estimated duration of one year, during which each patient will participate in 12 sessions divided into 3 weekly sessions for 4 weeks (see Figure 1). Once this phase of the study has been completed, patients who had been assigned to the placebo group will be offered the possibility of receiving the equivalent

“real” treatment at the MCC free of charge. Patients who received SMT may continue at their own cost. In addition, 4 weeks after the end of the study, patients will be contacted to request that they provide data on their pain intensity and disability, as described above, as well as responses to the questionnaires proposed as follow-up. Healthy volunteers will participate in two visits, baseline and follow-up after 4 weeks.

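### No adverse-effect form is planned after session 12, or after the last session of a patient who stops attending without notice

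*Protocol*

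**What the plan says.** The Protocol sets out one route for collecting adverse effects, under Adverse events reporting: "At the beginning of any of the follow-up SMT or placebo sessions, each patient will complete an online questionnaire". The form is retrospective. Onset is coded by "whether they were triggered immediately, up to 24 hours, or more than 24 hours after the previous session", and the longest duration categories are "between 24 and 48 hours, or longer than 48 hours".

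Procedures fixes the exposure: "each patient will participate in 12 sessions divided into 3 weekly sessions for 4 weeks". The same section describes one contact after treatment: "4 weeks after the end of the study, patients will be contacted to request that they provide data on their pain intensity and disability", "as well as responses to the questionnaires proposed as follow-up". It does not name adverse effects or say which questionnaires are meant. It also allows placebo patients to take up the real treatment, and SMT patients to continue at their own cost, once the treatment phase is over.

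Three other provisions bear on the point:

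- Experimental design (Protocol) says in general that all variables are measured before the first session and at the end of the twelfth.
- The alert rule under Adverse events reporting is triggered by a 3-point rise in pain score, or by moderate to severe events reported at three visits in a row.
- Statistical analyses (SAP) lists the number and severity of adverse effects among the exploratory variables compared between SMT and placebo.

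Neither document says what is collected from a patient who stops attending.

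**The concern.** A form completed at the start of a session can only report on what came before it. The last session a patient receives therefore has no form behind it. For a completer that is session 12. For a patient who leaves without notice it is whichever session came last, and if a reaction made the patient leave, it is the session that caused the reaction.

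The Protocol's own categories show that it expects effects in the uncovered period, because it provides for onset more than 24 hours after a session and duration beyond 48 hours.

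Two things are at stake: a complete account of harms in a trial of a manual treatment, and a fair comparison of adverse effects between the arms. The primary outcomes, pain intensity and disability, are not affected.

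**Working it through.** **Inputs**

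- Sessions per patient: 3 per week × 4 weeks = 12 (Protocol, Procedures).
- Patients: 50 per treatment arm, 100 in all (Protocol, Sample size calculation).
- Form timing: start of each follow-up session, looking back to the previous one (Protocol, Adverse events reporting).
- Dropout: not given in either document. A range of 0% to 20% is assumed below, with stops after session 1 to 6.

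The plan states no coverage figure, so there is nothing to reproduce first.

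**Step 1: coverage per patient.** A patient who receives k sessions completes forms at sessions 2 to k, and these cover sessions 1 to k − 1. One session, the last, is uncovered. For a completer, 11 of 12 are covered (91.7%). A patient who stops after session 1 has 0 of 1 covered.

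The number uncovered is at most one per patient. It is zero for a patient who completes the form at a visit and is then stopped before treatment that day. A patient who misses a visit and later returns is asked on return.

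**Step 2: full attendance.** Delivered: 50 × 12 = 600 per arm, 1,200 in all. Uncovered: 50 per arm, 100 in all. Share: 50/600 = 100/1,200 = 8.3%.

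**Step 3: with dropout.** If d of the 50 patients in an arm stop silently after session k, delivered sessions are (50 − d) × 12 + d × k. The uncovered count stays at 50.

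| Assumed stops per arm | After session | Delivered | Uncovered share |
|---|---|---|---|
| 5 (10%) | 6 | 45 × 12 + 5 × 6 = 570 | 50/570 = 8.8% |
| 5 (10%) | 1 | 45 × 12 + 5 × 1 = 545 | 50/545 = 9.2% |
| 10 (20%) | 6 | 40 × 12 + 10 × 6 = 540 | 50/540 = 9.3% |
| 10 (20%) | 1 | 40 × 12 + 10 × 1 = 490 | 50/490 = 10.2% |

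The share barely moves. What changes is which session goes unobserved.

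**Step 4: effect on the between-arm comparison.** Take the session-12 gap alone, with a constant effect rate per session in each arm. Both arms' counts are then multiplied by 11/12. The ratio between arms is unchanged, and the totals (and so the absolute difference) are understated by 1/12, or 8.3%.

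Now let a patients in the SMT arm and b in the placebo arm leave because of a reaction that no form captures. The observed difference in counts falls short of the true one by a further a − b. That moves toward no difference if a exceeds b, when SMT truly has more reactions. If a = b, the difference in counts is not shifted by this route. The documents give no basis for setting a or b.

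**Step 5: could another provision fill the gap?**

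- The general end-of-session-12 measurement, if it includes adverse effects, could catch immediate effects of that session. It cannot catch onset after 24 hours or duration past 48 hours.
- The 4-week contact does not name adverse effects. If the undefined questionnaires were meant to include them, recall would be over four weeks rather than the two to three days that separate sessions, and further SMT may already have begun.

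**The case against.** The strongest reply is that the gap is narrow and partly covered. Immediate effects of session 12 may be caught by the general measurement at the end of that session. The follow-up questionnaires are undefined and might include the form. Figure 1, the study schedule, could not be read in the text available and should be checked. Increased pain is one of the Protocol's adverse-effect categories, and pain and disability are asked for again four weeks later, so a persistent worsening would show there, though not labelled as an adverse effect. The comparison affected is exploratory.

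Most of this stands, and it limits the point. It does not remove it: no provision names adverse effects after session 12, and none covers a patient who stops attending.

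A reader might also infer stronger things that the documents do not support:

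- *Effects of session 12 are never recorded.* The text supports only that no collection of delayed or lasting effects is planned. Immediate effects may be caught, and spontaneous reports remain possible.
- *Dropouts add further lost reports to the 100.* They do not. A patient who stops loses the report on the last session received instead of session 12, not as well as it.
- *Patients stopped at the alert interview are lost too.* They have already completed that visit's form. An uncovered session arises only if treatment is still given that day.
- *The comparison is biased toward no difference.* This is conditional, as step 4 shows. The session-12 gap falls on both arms alike.

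**Conclusion.** The point holds as a gap in planned data collection. Followed as written, the form covers sessions 1 to 11 for a completer, and all but the last session for a patient who stops silently. The size is 100 of 1,200 patient-sessions (8.3%) with full attendance. It is roughly 8.8% to 10.2% under the assumed 10% to 20% dropout after sessions 1 to 6, with the uncovered count still at most 100.

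The definite consequence is an understated total burden of adverse effects. Bias of the arm comparison toward no difference depends on an assumption the documents cannot confirm: that patients stop because of reactions more often under SMT. The adverse-event part of the alert does not compensate, since a patient who leaves after one bad reaction cannot reach three visits in a row. The change is worth making because it is cheap and improves both the safety record and the planned comparison.

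**What to change.** All changes concern data collection only.

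1. In Protocol, Adverse events reporting, send the existing online form once after session 12, at about the usual between-session interval and before any further treatment is given.
2. In the same section, send the form to any patient who misses a session or stops, covering the last session received. Recording the reason for stopping, where the patient gives one, would let the condition for bias be examined by arm.
3. In Protocol, Procedures, state whether the 4-week contact asks about adverse effects. If it does, record the onset date and any SMT received after the trial, so that events can be attributed.

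If the forms are returned, coverage becomes 12 of 12 sessions for a completer and k of k for a patient who stops after session k.

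The cost is one more send of an existing form per patient, slight added burden, some non-response (probably highest among those who stopped), and a little staff time to reach non-attenders. No visit or procedure is added.
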